### *Effectiveness*

***Secondary Objective 4: Rate of successful conversion to sinus rhythm for at least one minute within 90 minutes from the start of first vernakalant IV administration will be expressed as the proportion of patients with successful conversion, together with the associated 95% confidence interval. Time (in hours) from start of vernakalant infusion to patient discharge/end of medical encounter will be summarized using appropriate measures of dispersion and central tendency (means, medians, ranges and standard deviations).*** These summaries will be reported overall and stratified by method of patient enrollment.

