2.2 Secondary Objectives

The secondary objectives of the study are to:

1. Summarise the count and rate of all SAEs for HOIs that may not meet the definitions of medically significant HOIs, as well as all other SAEs reported during treatment and during the first 24 hours after the last infusion of vernakalant IV or until discharge/end of medical encounter, whichever occurs earlier.
2. Characterise patients administered vernakalant IV in terms of patient demographics, medical history, and presenting conditions. Specific conditions to be summarised include:

- Heart failure, New York Heart Association (NYHA) functional class
- Prolonged QT, severe bradycardia, sinus node dysfunction, second or third degree heart block, clinically meaningful valvular stenosis, hypertrophic obstructive cardiomyopathy, restrictive cardiomyopathy, constrictive pericarditis
- History of hyperthyroidism
- Severe aortic stenosis, low systolic blood pressure (BP)
- Recent acute coronary syndrome (including myocardial infarction [MI])
- Presence of pacemaker/year of implantation
- Hepatic impairment

3. Document the administration of concomitant treatment modalities to restore or maintain sinus rhythm during the hospitalisation/medical encounter (e.g., oral or IV anti-arrhythmics, electrical cardioversion, ablation, Maze procedure).
4. Describe the rate of successful cardioversion to sinus rhythm for at least one minute within 90 minutes of start of first vernakalant IV administration and time (in hours) from vernakalant infusion until discharge/end of medical encounter.

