3.4 Derived Variable Definitions

The following derived/calculated values will be used:

- Age at enrolment = [(date of informed consent – date of birth) + 1]/365.25, or self-reported age if date of birth is not available.
- BMI = Weight (Kg)/Height (m)². English standard units should be converted to international or metric units.
- (S)AE or HOI onset in days and time (in hours or minutes) following vernakalant IV infusion = date/time of onset or (S)AE-date – date/time of start of first infusion.
- Duration or period = (stop time – start time). Note there are key durations that include, but are not limited to, duration of vernakalant IV infusions and duration of HOI and SAE.
- Vernakalant IV dose per body weight = vernakalant IV dose (mg) / body weight (kg).
- Duration of time to conversion to sinus rhythm = (date/time of conversion to sinus rhythm – date/time of start of first infusion).
- Percentage of weight-based dosing recommendation per label (%) = (Vernakalant IV dose [mg/kg] / Recommended vernakalant IV dose [mg/kg]) * 100. Range from 0% to above 100%, with 100% indicating that dose is equal to recommended dose, calculated per first or second infusion. Patients with cumulative doses greater than the maximum recommended dose will be noted (overall and for first and second infusion, separately).
- Duration of current AF in hours = (Vernakalant administration date/time - AF onset date/time).

- Time since first AF diagnosis = (Start date of Vernakalant IV administration - Date of first AF diagnosis).
- Rate of conversion to sinus rhythm for at least one minute within 90 minutes of start of first vernakalant IV administration = (Number of relevant patients converted to sinus rhythm for at least one minute within 90 minutes of start of first vernakalant IV administration) / (Total number of relevant patients administered vernakalant IV). Rate of conversion can be evaluated based on different types of patients, e.g. all patients receiving vernakalant IV or all such patients with other restrictions.
- Elevated liver enzymes (inclusive of possible abnormal liver function or liver injury) = an increase above upper limit of normal (ULN) for alanine aminotransferase (ALT), aspartate aminotransferase (AST), or total bilirubin (TB) or conjugated bilirubin. [1,2]
- Total hospital length of stay (hours) = (Date/time of discharge or release of facility – Date/time of hospital admission).

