5.4 Primary Objective # 1: Incidence of HOIs

Based on the primary objective #1, the incidence of HOIs reported from the start of first infusion through the first 24 hours following the last infusion of vernakalant IV or until discharge/end of medical encounter (whichever occurs earlier) will be calculated as the number of patients who have at least one specific pre-specified event starting from the beginning of the study period, divided by total number of patients enrolled and treated with vernakalant, multiplied by 100. The incidence of HOIs as designated by the investigator is summarised by method of enrolment (overall, prospective and retrospective) in **Table 8.1.1** to **Table 8.1.3** and the incidence of HOIs as designated by the SRC by method of enrolment (overall, prospective and retrospective) are displayed in **Table 8.2.1** to **Table 8.2.3**. The incidence of HOIs as designated by either the investigator or the SRC by method of enrolment (overall, prospective and retrospective) is displayed in **Table 8.3.1** to **Table 8.3.3**. Patients with more than one HOI will be counted once in the numerator. Patients with more than one HOI event (either more than one HOI within the same HOI type, or multiple HOI types) will be identified in the report, along with a footnote in the Table 8 series.

Results from the SRC review, including the SRC's classification of the event and whether the event qualifies as a study-defined HOI, are included in some of the HOI and SAE tables and listings (**Listings 1a, 2a, 7, and 8**). A listing of all SAEs and HOIs, both defined by the investigator and by the SRC, is shown in **Listing A**.

Definitions for HOIs (significant hypotension, significant ventricular arrhythmia, significant atrial flutter, and significant bradycardia) are provided in Section 3.1. For the HOI significant bradycardia, the incidence of bradycardia requiring electrical pacing (temporary or permanent) and the incidence of patients experiencing any other SAEs involving bradycardia (but not

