requiring temporary or permanent pacing) will be reported both separately and combined. A study definition of SAEs involving bradycardia is conservatively added to the investigator assessment based on a list of MedDRA terms that would be considered to be SAEs involving bradycardia (**Appendix 2**). Therefore “investigator assessment” includes bradycardia HOIs designated as such per the investigator and/or study definition. MedDRA code version 14.0 used to identify SAEs are consistent with clinical development program.

For patients who receive one infusion during a treatment episode, the follow-up period for HOIs is from the start of this infusion through the first 24 hours, or until discharge/end of medical encounter, whichever occurs earlier.

For patients who receive more than one infusion during a treatment episode, the follow-up period for HOIs is from the start of the first infusion through the first 24 hours following the start of the last infusion, or until discharge/end of medical encounter, whichever occurs earlier.

Because HOIs are expected to be rare events, Clopper Pearson (Exact) confidence intervals will be constructed around the point estimate of the incidence for each HOI. [3] Numbers and rates of HOIs will also be presented according to time intervals since start of first vernakalant infusion, i.e., 0 to less than 2 hours, 2 to less than 4 hours, and 4 hours to a maximum of 24 hours.

The primary analysis for HOI incidence is the 0-2 hour post infusion time point. Given the lower expected sample size, vernakalant's mode of action and the non-interventional nature of the study design, the 2-4 hour and 4-24 hour post infusion time points are considered secondary and tertiary analyses, respectively.

The HOI incidence for each time interval will be calculated as follows.

For each time interval, the numerator will be the number of patients with at least one HOI with an onset date and time in the time interval occurring among patients enrolled and treated with vernakalant. The denominator will be the number of patients enrolled and treated with vernakalant.

For the 0-<2 hour time interval, the number of patients with at least one HOI with an onset date and time in the 0-2 hour interval (interval is from start date and time of vernakalant administration to 1:59:59 following start date and time of vernakalant administration) divided by the number of patients enrolled and treated with vernakalant.

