5.10 Secondary Objective #4: Rate of Conversion to Sinus Rhythm

For patients in the analysis population set and the effectiveness analysis population set, the rate of successful conversion to sinus rhythm for at least one minute within 90 minutes from the start of first vernakalant IV administration (Secondary Objective 4) will be expressed as the proportion of patients with successful conversion, together with the associated 95% confidence interval. (**Table 15a**). The rate of successful conversion to sinus rhythm without time restriction will also be expressed as the proportion of patients with successful conversion, together with the associated 95% confidence interval. The time (in minutes) from start of vernakalant infusion to conversion to sinus rhythm among those patients who converted will be summarised using appropriate measures of dispersion and central tendency (means, medians, ranges, Q1-Q3 ranges, and standard deviations) (**Figure 3**). As defined in Section 4.3, a pre-specified secondary analysis of the effectiveness of vernakalant will be restricted to a subgroup of patients who receive vernakalant IV in accordance with the SmPC (i.e., adult indication, therapeutic indication for AF, duration of AD \leq 7 days for non-surgery patients and \leq 3 days for post-cardiac surgery patients, and no contraindications) (**Table 15b**). Rates of successful conversion will also be

tabulated for all patients by non-surgery and post-cardiac surgery indications, respectively (**Table 15c, 15d**).

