| Significant Atrial Flutter | xx | x.x (x.xx – x.xx) | xx | xx | x.x (x.xx – x.xx) | xx | xx | x.x (x.xx – x.xx) | xx | xx | x.x (x.xx – x.xx) | xx |
| Significant Bradycardia ^{3, 4} | xx | x.x (x.xx – x.xx) | xx | xx | x.x (x.xx – x.xx) | xx | xx | x.x (x.xx – x.xx) | xx | xx | x.x (x.xx – x.xx) | xx |
| Bradycardia Requiring | xx | x.x | xx | xx | x.x | xx | xx | x.x | xx | xx | x.x | xx |

| | Time Since First Vernakalant Infusion | | | | | | | | | | | |
|--|--|------------------------------------|-------------|---|---------------------------------------|-------------|--|------------------------------------|-------------|--------------------|---------------------------------------|-------------|
| | 0 - < 2 hours from start of first infusion (N=xxx) ¹ | | | 2- < 4 hours from start of first infusion (N=xxx) ¹ | | | 4- 24 hours from start of first infusion (N=xxx) ¹ | | | Overall (N=xxx) | | |
| HOI | Patients n | Incidence (95% CI) ² | Events n | Patients n | Incidence (95% CI) ² | Events n | Patients n | Incidence (95% CI) ² | Events n | Patients n | Incidence (95% CI) ² | Events n |
| Electrical Pacing | | (x.xx – x.xx) | | | (x.xx – x.xx) | | | (x.xx – x.xx) | | | (x.xx – x.xx) | |
| SAE involving Bradycardia ⁵ | xx | x.x (x.xx – x.xx) | xx | xx | x.x (x.xx – x.xx) | xx | xx | x.x (x.xx – x.xx) | xx | xx | x.x (x.xx – x.xx) | xx |

¹For each time interval, the numerator will be the number of patients with at least one HOI with an onset date and time in the time interval occurring to any patients enrolled and treated with vernakalant. The denominator will be the total number of patients enrolled and treated.

²Incidence (95% confidence intervals) calculated as the number of patients who have a specific pre-specified event starting during the study period, divided by the total number of patients enrolled, multiplied by 100.

³According to the investigator, xx events were reported to include both bradycardia and hypotension. Therefore, each event was counted individually in both the hypotension and bradycardia SAE subtotals and in total number of events.

⁴Significant bradycardia defined as combination of bradycardia requiring electrical pacing (temporary or permanent) or any other serious adverse event reports involving bradycardia.

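### The 2-<4 h and 4-24 h HOI incidences in Table 8 are proportions of all treated patients, with no count of patients still observed, and the SAP drops the infusion-to-discharge summary that would show it (minor)

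*SAP*

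**What the plan says.** SAP 5.4 follows patients for HOIs from the start of the first infusion to 24 h (counted from the last infusion where there are several), or to discharge or end of the medical encounter if earlier. Overall incidence is the number of patients with an event "divided by total number of patients enrolled and treated with vernakalant". The same rule is then set for the intervals: "The denominator will be the number of patients enrolled and treated with vernakalant". It is repeated separately for 0-<2 h, 2-<4 h and 4-24 h. Footnote 1 of Table 8.1.1, attached to the N of each interval column, agrees: "The denominator will be the total number of patients enrolled and treated". Tables 8.2.1 and 8.3.1 carry equivalent footnotes. No Table 8 shell has a row or column for patients still under observation.

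The same section makes 0-2 h primary, 2-4 h secondary and 4-24 h tertiary. Its first reason is "Given the lower expected sample size"; protocol 10.2 gives the same reason. The protocol sets no interval denominator.

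On time to discharge, protocol 10.3 (Secondary Objective 4) says that the time "from start of vernakalant infusion to patient discharge/end of medical encounter will be summarized using appropriate measures of dispersion and central tendency", overall and by enrolment method. SAP 2.2 keeps this in the objectives: "time (in hours) from vernakalant infusion until discharge/end of medical encounter". SAP 5.10, the analysis section for that objective, covers conversion only: "The time (in minutes) from start of vernakalant infusion to conversion to sinus rhythm among those patients who converted will be summarised". The one stay variable in SAP 3.4, reported in Table 1.1, runs from hospital admission to discharge and is split at 24 h.

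**The concern.** The plan expects fewer patients in the later windows, yet every interval column carries the same N. A patient discharged 3 h after infusion enters the 4-24 h column as observed and event-free. If the column is read as the risk of a late event in patients under observation, the estimate and its upper limit are too favourable, and the table does not show by how much. The infusion-to-discharge summary would have let a reader judge this, but the SAP does not carry it through. Length of stay from admission only bounds post-infusion stay from above and cannot give the number present at 2 h or 4 h.

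This matters most when few events occur. With zero or one late HOI, the upper limit is the main message of the column, and its meaning depends on how many patients were there to have an event.

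**Working it through.** **Inputs.** Target N = 2,000 treatment episodes (SAP 4.1). Two-sided 95% Clopper-Pearson limits (SAP 5 and 5.4). The share still observed at the start of a late interval is not in the documents, so it is assumed, over a range.

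**Formula.** For x events in n: lower = Beta(0.025; x, n-x+1), upper = Beta(0.975; x+1, n-x). For x = 0 the upper limit is 1 - 0.025^(1/n).

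**The plan's own figure.** SAP 4.1, expected proportion 0.003 and N = 1,500: x = 4.5 gives 0.0009 to 0.0073, margin 0.0043. These round to the stated 0.001, 0.007 and 0.004. The limits in all 44 cells of SAP Table A reproduce.

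**Late interval, N = 2,000 treated.**

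| Denominator | n | Zero events: upper limit | One event: estimate (95% CI) |
|---|---|---|---|
| All treated (SAP) | 2,000 | 0.184% | 0.050% (0.001-0.278) |
| 90% observed (assumed) | 1,800 | 0.205% | 0.056% (0.001-0.309) |
| 50% observed (assumed) | 1,000 | 0.368% | 0.100% (0.003-0.556) |
| 30% observed (assumed) | 600 | 0.613% | 0.167% (0.004-0.925) |

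The upper limit grows by about 1/(share observed): 0.205/0.184 = 1.11, 0.368/0.184 = 2.0, 0.613/0.184 = 3.3. With zero events the estimate is 0 under either denominator, so only the limit moves.

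**By enrolment method.** Protocol Appendix I plans 435 retrospective patients, leaving 2,000 - 435 = 1,565 prospective. Zero-event upper limits at the same assumed shares are:
- prospective: 0.235% on all treated, against 0.262%, 0.471% and 0.782%;
- retrospective: 0.844% on all treated, against 0.937%, 1.678% and 2.798%.

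**Coverage.** For a true risk of 0.3% among patients still observed, the all-treated interval contains it with probability 0.96, 0.94, 0.80 or 0.44 if 90%, 75%, 50% or 25% are observed (assumed). With the observed denominator, coverage is at least 0.97 at each of these shares. At a true risk of 0.1% the all-treated interval does not lose coverage (0.98 or more throughout).

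**How many late events?** The pooled trials give 0 to 0.22% per HOI over 24 h in 889 patients (SAP 4.1). At 0.22%, 2,000 patients yield 0.0022 x 2,000 = 4.4 events. That is not a ceiling: 0.22% of 889 is 2 events, whose exact upper limit is 0.81%, or about 0.0081 x 2,000 = 16. Protocol 10.2 and SAP 3.1.4 also expect somewhat higher rates here.

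**Limits of the number observed at 4 h.** Two assumed cases:
- If 1,000 are present at 4 h and half leave evenly by 24 h, observation amounts to 1,000 x (1 - 0.5/2) = 750 full intervals. The zero-event upper limit is then 0.491%, not 0.368%, so the count at 4 h still gives an optimistic limit.
- If discharged patients have r times the risk of those who stay, then with one event and half observed the all-treated risk is 0.100% x (0.5 + 0.5r): 0.050%, 0.075% or 0.100% for r = 0, 0.5 or 1. The figure on observed patients overstates it unless r = 1.

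**The case against.** The strongest reply is that nothing here is miscalculated. Primary Objective 1 itself ends observation at discharge, so the share of treated patients with a reported HOI answers it. The denominator is stated in the text and in the footnotes. The affected windows are already ranked secondary and tertiary, and the protocol background explains the focus on the first 2 h by rapid clearance and peak exposure. All of this stands, and the all-treated figure should stay.

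A reader might infer more: that the planned HOI incidence is wrong, that the primary result is biased, or that late limits are understated severalfold. The documents support none of these. The estimate is valid for what it is. The 0-<2 h column is touched only by discharges within 2 h. Any multiple depends on a discharge pattern that the documents do not give; at 90% observed the zero-event limit moves only from 0.184% to 0.205%.

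On the missing summary, SAP 5.11 promises that the analyses will address every objective, which would include time to discharge. That is a fair reply as to intent. It does not supply a derived variable, analysis text or table shell.

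**Conclusion.** The point holds as a gap in reporting. In the 2-<4 h and 4-24 h columns, Table 8 gives a proportion of all treated patients without the number still observed. Read as a risk among observed patients, non-zero estimates and the exact upper limits are too low by roughly 1/(share observed). The size in this study cannot be computed from the documents; the 0.205% to 0.613% range against 0.184% rests wholly on assumed shares of 90% to 30%. The pooled-trial rates suggest few late events but do not cap them.

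The firmest part rests on no assumption: protocol 10.3 plans the infusion-to-discharge summary, SAP 2.2 lists it, and SAP 3.4, 5.10 and the table shells do not deliver it. Severity is minor, since only the secondary and tertiary windows are materially affected.

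**What to change.** Amend the SAP as follows:

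- **(a) Label.** Keep the all-treated proportion and label it *HOIs reported before discharge, all treated*.
- **(b) Numbers observed.** Add to the Table 8 series the number under observation at 2 h and at 4 h after the start of the first infusion, with incidence and Clopper-Pearson limits on that number. Count separately the patients whose infusion or discharge time is missing. Note that the 4-24 h limit is still optimistic because patients leave during the interval, and that it does not estimate the all-treated risk if discharge is informative.
- **(c) Time to discharge.** Carry the protocol 10.3 summary into SAP 3.4, SAP 5.10 and one table, overall and by enrolment method.

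I would not add a cumulative incidence censored at discharge: it gives no usable limit with zero events and needs discharge to be non-informative.

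The cost is small programming work, since discharge date and time are already collected (protocol 7.1.1), and two denominators in Table 8, which need clear labels. Later-interval limits will look less favourable. The protocol, the interval definitions, the primary window and the no-imputation rule do not change.

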## Vernakalant IV Sterile Concentrate Prospective Safety Registry Study

Sponsor Protocol Identifier: 6621-049-00

3 August 2016

---

unique to this technique, including skin burns, complications of sedation and malfunctions of a pacemaker or internal defibrillator. [Ref. 5.4: 104]

The potential adverse events of both electrical and pharmacological cardioversion and the limited efficacy of pharmacological cardioversion have warranted the development of novel therapeutic options. [Ref. 5.4: 371, 441]

Vernakalant, a medicine that acts preferentially in the atria, has a novel and unique mechanism of action. Controlled clinical trials [Ref. 5.4: 441] of vernakalant IV have been conducted to define the efficacy and safety profile of vernakalant IV. Two phase III randomised trials demonstrated that the conversion rate of recent onset ( $\leq 7$  days) AF to sinus rhythm was significantly better for Vernakalant compared to placebo (51.1% versus 3.8%, respectively;  $p<0.0001$ ) with an open-label trial demonstrating a conversion rate of 50.9%. [Ref. 5.4: 442] Another phase III randomised trial of post-cardiac surgery patients (CAD and/or VHD) demonstrated that Vernakalant was significantly better compared to placebo in the conversion of recent onset ( $\leq 3$  days) AF to sinus rhythm (47% versus 14%, respectively;  $p<0.001$ ). [Ref. 5.4: 210] In patients who converted to sinus rhythm, the median time to conversion was 11-13 minutes in those studies.

Clinically significant adverse reactions occurred infrequently. Clinically significant adverse reactions observed in the clinical program and described in detail in the Summary of Product Characteristics (SmPC) included: hypotension, ventricular arrhythmia, atrial flutter and bradycardia. Incidence rates for these adverse reactions are presented below, using pooled data from the placebo-controlled phase 2 and phase 3 clinical trials (773 patients received vernakalant, 335 received placebo). Because vernakalant IV is rapidly cleared from the circulation, adverse events from the start of infusion through the first 2 hours after infusion are considered, as these occur during the period of peak vernakalant exposure.

Adverse Reaction	Vernakalant	Placebo	$\Delta$ (95%CI)
Hypotension	7.6%	5.1%	2.5 (-0.6, 5.6)
CHF subpopulation	16.1%	4.7%	11.4 (3.3, 19.4)
Clinically meaningful hypotension*	1.2%	0%	---
CHF subpopulation	2.9%	0%	---
Ventricular arrhythmia	3.9%	3.2%	0.8 (-1.6, 3.2)

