**Vernakalant IV Sterile Concentrate Prospective Safety Registry Study**

Sponsor Protocol Identifier: 6621-049-00

3 August 2016

---

retrospective) and unadjusted incidence and 95% confidence interval will be reported. In addition, results will also be reported separately by method of enrolment. Results will be calculated for the combined endpoint of (1) bradycardia requiring electrical pacing (temporary or permanent) or (2) any other serious adverse events reports involving bradycardia, and for each endpoint separately.

Numbers and rates of HOIs will also be presented according to time intervals since start of vernakalant IV administration, i.e., 0 to less than 2 hours, 2 to less than 4 hours, and 4 hours to a maximum of 24 hours. Characteristics of patients with HOIs, which may include prior medical history, presenting conditions, medication use, dosing/administration of vernakalant IV, and concomitant therapies, and assessment of relatedness as provided by the investigator will be summarised in a listing of individual HOI events in study reports. Case narratives will also be provided for each HOI.

The primary analysis for HOI incidence is the 0-2 hour post infusion timepoint. Given the lower expected sample size, vernakalant's mode of action and the non-interventional nature of the study design, the 2-4 and 4-24 hour post infusion timepoints are considered secondary and tertiary analyses, respectively.

It is anticipated that rates of HOIs may be somewhat higher in this real-world study setting compared to rates observed in the vernakalant clinical trial program due to the selective patient entry criteria of these randomized clinical trials. Likewise, comparisons to the published literature are not planned and would prove difficult due to differences in case definitions for each specific HOI and variability of reported follow-up periods from administration of a given study drug or intervention to time of the event. However, the frequency of HOIs will be carefully monitored by the Sponsor, the CRO, and the independent Safety Review Committee throughout the duration of the registry study.

***Primary Objective 2: In order to investigate the potential risk of overdose and medication error, describe vernakalant IV administration/dosing by summarising patient body weight, total dose with each IV infusion, and length of time for each IV infusion.***

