For the 2-<4 hour time interval, the number of patients with at least HOI with an onset date and time in the 2-<4 hour interval (interval is from 2:00:00 following start date and time of vernakalant administration to 3:59:59 following start date and time of vernakalant administration) divided by the number of patients enrolled and treated with vernakalant.

For 4-24 hour time interval, the number of patients with at least one HOI with an onset date and time in the 4-24 hour interval (interval is from 4:00:00 following start date and time of vernakalant administration to 24:00:00 following start date and time of vernakalant administration) divided by the number of patients enrolled and treated with vernakalant

Characteristics of patients with HOIs, which may include prior medical history, presenting conditions, medication use, dosing/administration of vernakalant IV, concomitant therapies, and assessment of relatedness as provided by the investigator will be summarised as a narrative in the listing of individual HOI events in study reports. Case narratives will be provided in **Listing 1b** and **Listing 2b** for each HOI and SAE regardless of the relationship to vernakalant and will describe patients with more than one HOI event reported. Listings will be by-event (i.e., patient with multiple events will be repeated for each event type) and will contain the patient's case narrative for each event type.

5.5 Primary Objective #2: Administration of Vernakalant Consistent with Weight-Based Dosing and Patient Monitoring

Based on Primary Objective #2, distributions of patient body weight, number of infusions, total dose administered with each IV infusion and administration duration stratified by body weight (<113 kg and \geq 113 kg) will be summarised (**Table 9**). Body weight and details of dosing and administration (indication, number of infusions, dose in mg and mg/kg, percentage of weight-based dosing recommendations, duration, whether stopped prematurely, and the reasons for stopping) will be presented separately for each body weight group.

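### HOI intervals are timed from the first infusion but follow-up ends relative to the last, so part of follow-up falls in no interval and some onsets after a second infusion miss the primary window

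*SAP*

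**What the plan says.** SAP 5.4 breaks HOI incidence down by time: "Numbers and rates of HOIs will also be presented according to time intervals since start of first vernakalant infusion". The 0-<2 h interval is worked out as "interval is from start date and time of vernakalant administration to 1:59:59 following start date and time of vernakalant administration", and the last one as "interval is from 4:00:00 following start date and time of vernakalant administration to 24:00:00 following start date and time of vernakalant administration". These two rules alone do not say which infusion is meant. The first quotation does, and so do the onset derivation in SAP 3.4 and the column headers of Tables 8, 16.3 and 17: it is the first.

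The same section ranks the intervals: "The primary analysis for HOI incidence is the 0-2 hour post infusion time point". Protocol 10.2 has almost the same sentence, "The primary analysis for HOI incidence is the 0-2 hour post infusion timepoint". Just before it, the protocol counts the intervals from the start of administration with the same cut points.

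The end of follow-up appears twice in SAP 5.4. The incidence definition runs "through the first 24 hours following the last infusion of vernakalant IV". The paragraph on patients with more than one infusion runs "through the first 24 hours following the start of the last infusion". Both stop earlier at discharge or end of encounter.

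More than one infusion is expected. SAP 5.1.1 allows several per treatment episode, SAP 5.5 describes an initial and a second infusion, and Table 9.1 has a row for more than two.

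**The concern.** Two clocks are in use. The intervals run from the first infusion, while the end of follow-up depends on the last. For a one-infusion patient they agree, apart from the ambiguity over whether 24 h is counted from the start or the end of that infusion. For a patient with two or more infusions they separate at both ends.

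- **Late end.** Follow-up can continue past 24:00:00 from the first start. An HOI there counts under Overall and in none of the three intervals.
- **Early end.** An HOI soon after a late second infusion, but 2 h or more after the first start, is filed as a secondary or tertiary result although it follows closely on exposure.

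The phrase *post infusion* in the primary-analysis sentence adds to the uncertainty, since it does not say which infusion, or whether its start or end. What is at stake is the meaning of the primary estimate for primary objective 1, and whether the columns of Table 8 can be reconciled.

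**Working it through.** **The plan's own figure.** The documents give no number for this mismatch. The nearest figure is the precision example in SAP 4.1: expected proportion 0.003, N = 1,500, limits 0.001 and 0.007, margin 0.004. Clopper-Pearson with x = 0.003 × 1,500 = 4.5 gives 0.00090 to 0.00729 and a margin of 0.00429, so it reproduces, as do all 44 cells of Table A. It serves here only for scale.

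**Inputs**
- Each infusion lasts 10 min (SAP 5.5).
- Intervals run from the first start and close at 24:00:00 (SAP 5.4).
- Follow-up ends 24 h after the last infusion or after its start (SAP 5.4).
- The gap g between infusions is collected (Protocol 7.1.1), but no value is given. It is assumed here to be 0 to 110 min.

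**Formulas**, in minutes from the first start, for two infusions
- Second infusion starts at 10+g and ends at 20+g.
- Of the 120 min after the second start, the part outside the primary interval is 120 − (120 − (10+g)) = 10+g, up to 120.
- Follow-up in no interval: 10+g if it ends 24 h after the second start, 20+g if it ends 24 h after the second end. This applies only to patients still in the encounter.

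| g (min) | Outside primary interval, of 120 | Inside | In no interval, start / end reading |
|---|---|---|---|
| 0 | 10 (8%) | 110 | 10 / 20 |
| 15 | 25 (21%) | 95 | 25 / 35 |
| 30 | 40 (33%) | 80 | 40 / 50 |
| 60 | 70 (58%) | 50 | 70 / 80 |
| 110 | 120 (100%) | 0 | 120 / 130 |

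**Illustration of the effect on the primary count.** Take the HOIs with onset from the first start to 2 h after the second start, and let q be the share with onset after the second start. The share of these HOIs missing from the 0-<2 h count is q × f, where f is the fraction of post-second-start onsets that fall beyond 2 h from the first start. The range q = 20% to 50% and both onset patterns are assumptions.

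- Flat onset over the 120 min: f = (10+g)/120. For g = 15, f = 0.208 and the loss is 4% to 10%. For g = 60, f = 0.583 and the loss is 12% to 29%.
- Early onset, exponential with median 12 min, λ = ln 2/12: f = [exp(−λ(110−g)) − exp(−120λ)] / [1 − exp(−120λ)]. For g = 15, f = 0.0032 and the loss is about 0.1% to 0.2%. For g = 60, f = 0.0548 and the loss is about 1% to 3%.

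**Scale of one event.** At the top of the trial range, 0.22% × 2,000 = 4.4 patients per HOI, so one moved event is 1/4.4 = 23% of that count. In absolute terms it is 1/2,000 = 0.05 percentage points, against a Table A margin of 0.3 points at 0.002 and N = 2,000.

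**The case against.** The strongest reply is that a fixed window from the first start is a legitimate choice. It gives every patient the same time zero and the same window length. A window tied to the last infusion has a length set by a treatment decision made after time zero. The table shells already refer to reported events (Table 8.3.1, footnote 4; the note under Table 16.1a.3), so replacing the primary definition now would be a change made with data in view. All of this stands, and it is why the first-infusion window should remain primary.

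Several stronger readings are tempting, and the documents do not support them.

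- *A reader might infer that the SAP departs from the protocol.* Protocol 10.2 counts the intervals from the start of administration with the same cut points. The loose wording is in both documents.
- *A reader might take Protocol Section 3 as the specification of the primary window.* It says "adverse events from the start of infusion through the first 2 hours after infusion are considered", but as background to the pooled-trial table, and it does not say the last infusion. Protocol 10.2 gives its own reasons for ranking the intervals.
- *A reader might infer that all events after a second infusion leave the primary window.* Only onsets 2 h or more after the first start do. With a 15-minute gap, 95 of the 120 minutes stay inside.
- *A reader might infer that HOIs are lost.* The Overall column covers the whole of follow-up with its own confidence interval, and the listings and narratives show every event.
- *A reader might see a spoiled comparison with the trial rates.* The clinically meaningful events in Section 3 are not the HOIs, and the trial rates for the HOIs in Protocol 10.7 are 24-hour rates.

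**Conclusion.** The point holds as a definition problem shared by both documents. For patients with more than one infusion who are still under observation, 10+g minutes of follow-up (20+g under the other reading) lie in no interval, so the event counts by interval need not add up to Overall. A further 10+g of the 120 minutes after the second start lie outside the primary interval.

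Any effect on the primary estimate is downward, because the first-infusion clock can only remove such events from 0-<2 h. A material bias cannot be claimed. The geometry rests on the 10-minute infusion length in SAP 5.5. The gaps, the share of patients with a second infusion and the onset pattern are not in the documents. Protocol Section 3 reports that hypotension in the trials typically arose during or early after infusion; if that holds for the HOIs and gaps are short, the effect is probably small. Long gaps or later onset would make it larger.

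**What to change.** 1. In SAP 5.4, use one end of follow-up in both the incidence definition and the paragraph on more than one infusion.
2. Close the last interval at that end instead of at 24:00:00 from the first start, in SAP 5.4 and in Tables 8, 16.3 and 17, so that every HOI in follow-up falls in an interval.
3. State in Protocol 10.2 and SAP 5.4 that the primary 0-2 h window runs from the start of the first infusion.
4. Add a sensitivity version of Table 8 whose first window runs from the start of the first infusion to 2 h after the start of the last. Keep the first-infusion table as primary, for continuity with the interim reports.

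The sensitivity window should use start times. Protocol 7.1.1 collects them for each infusion, while Protocol 7.2.1 lists stop times among the items that may be unavailable retrospectively, and SAP 4.4 rules out imputing them. Footnotes to Tables 7.1, 12a.1 and 13a.1 also allow for missing administration times in retrospective patients, so the new table should show how many patients could not be placed.

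The cost is a few sentences, a little extra programming, and a sensitivity estimate that may be slightly less favourable.
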